11 TREATMENT PLAN

11.1 INVESTIGATIONAL AGENTS

Blinded supplies of ondansetron and/or matched placebo capsules will be dispensed by the research pharmacist or investigator weekly for twice daily administration in subjects for 8 weeks. Subjects will be instructed that capsules may be taken without regard to meals and to take two pills daily, one between 8:00 and 10:00 a.m. and one between 6:00 and 8:00 p.m.

11.2 COGNITIVE BEHAVIORAL THERAPY

The CBT program during the 8-week medication treatment phase of the study will consist of thrice weekly 90-minute group sessions. However, in order to help potential participants to stop methamphetamine use, they will be introduced to the counselors and scheduled to attend two 60-minute early recovery skills groups each week after signing informed consent up until study

enrollment. Topics covered in this early recovery skills group include: Getting Rid of Paraphernalia; Triggers; Introduction to 12-Step Groups; and Brief Information on HIV (see Appendix II). Concepts presented in these sessions include the following: (1) self-monitoring and relapse analysis; (2) identification of "triggers" and cognitive strategies for coping with them; (3) teaching of problem solving skills; (4) education about methamphetamine and methamphetamine dependence; (5) education about HIV and reducing the risk of HIV transmission; and, (6) promotion of prosocial activities. The content of these group topics is prearranged and sequenced using a manualized format. This is a feasible treatment that is known to be well accepted by subjects and it represents an appropriate, ethically defensible standard treatment condition to serve as the "platform" for the medication trial. Staff members who provide CBT counseling will have attended training in the use of these materials. The CBT specialist will have a minimum of a master's degree (or equivalent) or a bachelor's degree plus counseling experience with substance users. To ensure that the integrity of these sessions is maintained, all sessions are audiotaped and reviewed centrally by the Principal Investigator or his designee. Our experience is that these sessions are valued by subjects and attendance is excellent. Thus, psychosocial involvement is seen as a standard or platform for the proposed pharmacotherapy evaluation.

12 STUDY PROCEDURES

12.1 SUBJECT RECRUITMENT

Interested candidates who are seeking treatment and are available to come to the clinic for 14-to-16 weeks will meet with the investigator or designated investigational staff and receive an explanation of the study purpose and requirements. If still interested after receiving an explanation of the study, the candidate will be given an opportunity to review, inquire about, and sign the informed consent form. If the study will be explained initially to the potential participant by investigational staff, a two-part consent form will be used with part one being consent to start screening procedures that do not include medical assessments such as blood collection and ECG. When an investigator or study physician has explained the study and answered the potential participants questions, part two of the consent form will be signed and the remaining medical procedures to be conducted during screening may be performed. Subjects are given a copy of the signed informed consent. Any participant who has difficulty understanding the information contained in the consent will be rescheduled and the consent process will be repeated. Research staff will work closely with the participant in an effort to help them understand the requirements of their participation. Persons with literacy problems will be assisted to the extent possible. Any participant who is unable to demonstrate understanding of the information contained in the informed consent will be excluded from study participation and assisted in finding other sources of treatment. Persons who are excluded, or who decline participation, will be given referrals to other resources in the area.

12.2 SCREENING/BASELINE ASSESSMENTS

After the subject has signed the informed consent form, the screening assessment process begins (which includes a two-week baseline assessment period). Assessments are described in section 13. Baseline assessments will occur over a two-week period. If a subject fails to provide a minimum of four completed Methamphetamine Withdrawal Questionnaires (MAWQ), at least

four urine specimens – including one positive for urine methamphetamine and the accompanying other baseline repeated measures within the required two-week period, the baseline period may be shifted or extended until the subject meets the requirements in any consecutive 14-day period but within 4-weeks before randomization. Screening assessments are considered valid if the subject enrolls on the study within 4 weeks. If the subject does not meet the requirements within the 4 weeks, then screening/baseline measures must be repeated before subject enrollment but must not be started until 30 days have elapsed after the last screening visit. An End of Trial CRF must be completed if the subject is a screen fail.

In order to help potential participants to stop methamphetamine use, they will be scheduled to attend two 60-minute early recovery skills groups each week. Topics covered in this early recovery skills group include Getting Rid of Paraphernalia; Triggers; Introduction to 12-Step Groups; and Brief Information on HIV (see Appendix II). Persons who fail to provide a minimum of four urine samples and to complete all required baseline data collection and procedures within a two-week period will not be randomized.

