TREATMENTS. Subjects will receive 0.25, 1.0, or 4.0 mg of ondansetron or placebo twice a day for 8 weeks. All subjects will receive manual-guided CBT three times per week throughout the 8 weeks of treatment.

SAFETY ASSESSMENTS: All candidates for study enrollment will have a physical examination, a 12-lead ECG, and clinical laboratory studies (blood chemistry, hematology, and urinalysis. If the potential participant is female, a pregnancy test will also be performed during screening, at study week 4, and at study termination. Vital signs, concomitant medication use, and a urine screen for other substances of abuse will be assessed weekly during treatment. Clinical laboratory studies will be performed at week 4 and at study termination. AEs will be assessed at each visit. An HIV Risk-Taking Behavior Scale (HRBS) will be used to characterize the population HIV risk behaviors (baseline and at study termination). At study termination (the last assessment visit after treatment completion or if the subject terminates prematurely), subjects

Version No.: 3, Date: 22 May 2002

will be evaluated for AEs, vital signs, physical examination, clinical laboratory studies, and electrocardiogram (ECG).

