9.1 INCLUSION CRITERIA

Potential subjects must:

- 1. Be at least 18 years-of-age.
- 2. Have a DSM-IV diagnosis of methamphetamine dependence as determined by SCID.
- 3. Be seeking treatment for methamphetamine dependence.
- 4. Have at least 1 methamphetamine or amphetamine positive urine specimen (> 1000 ng/mL) within the two-week baseline period prior to randomization with a minimum of 4 samples tested.
- 5. Be able to verbalize understanding of consent form, able to provide written informed consent, and verbalize willingness to complete study procedures.
- 6. Be female and have a negative pregnancy test and agree to use one of the following methods of birth control, or be postmenopausal, have had a hysterectomy or have been sterilized, or be male.
 - a. oral contraceptives
 - b. barrier (diaphragm or condom) with spermicide or condom only
 - c. intrauterine progesterone or non-hormonal contraceptive system
 - d. levonorgestrel implant
 - e. medroxyprogesterone acetate contraceptive injection
 - f. complete abstinence from sexual intercourse

NIDA-CTO-0011 Ondansetron for Methamphetamine Dependence

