- 14. Be using ondansetron or any medication that could interact adversely with ondansetron, within the following times of beginning of administration of ondansetron based on the longest time interval of A, B, and C, below or as otherwise specified:
 - A) Five half lives of other medication or active metabolite(s), whichever is longer
 - B) Two weeks
 - C) Interval recommended by other medication's product labeling

Medications/herbal supplements that fall into this category include any serotonin-active substances and drugs significantly metabolized by the P-450, such as:

- serotonin-active substances, i.e., sumitriptan (Imitrex), zolmitriptan (Zomig), cyproheptadine, citalopram, ketanserin, ritanserin, fluoxetine, paroxetine, sertraline, methysergide, ergotamine, ergonovine;
- psychoactive medications such as Neuroleptics;
- drugs significantly metabolized by the P-450, i.e., cimetidine, phenobarbital, St. John's Wort;
- herbals that enhance serotonergic effects, i.e., horehound.
- 15. Have participated in any experimental study within 8 weeks (the nature of excluded studies may be discussed with NIDA investigators).
- 16. Be pregnant or lactating.
- 17. Have clinically significant laboratory values (outside of normal limits), in the judgment of the investigator (Appendix I).
- 18. Have had electroconvulsive therapy within the past 90 days before screening.
- 19. Have had opiate-substitution therapy (methadone, LAAM, buprenorphine) within 2 months of enrollment.
- 20. Have a diagnosis of adult asthma, including those with a history of acute asthma within the past two years, and those with current or recent (past 2 years) treatment with inhaled or oral beta-agonist or steroid therapy (due to potential serious adverse interactions with methamphetamine).
- 21. Be actively using albuterol or other beta agonist medications, regardless of formal diagnosis of asthma. (Inhalers are sometimes used by methamphetamine users to enhance methamphetamine delivery to the lungs.) If respiratory disease is excluded and the subject will consent to discontinue agonist use, s/he may be considered for inclusion.

24

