10.6 SAFETY CONSIDERATIONS

The principal adverse events in U.S. clinical trials with 8 mg of ondansetron given orally b.i.d. are in order of frequency headache, malaise/fatigue, constipation, diarrhea, abdominal pain, xerostomia, and weakness. Rare cases of anaphylaxis, bronchospasm, tachycardia, angina, extrapyramidal reactions, rash, hypokalemia, electrocardiograph alterations, vascular occlusive effects, and grand mal seizures have been reported. With the exception of extrapyramidal reactions, rash, analphylaxis, and bronchospasm, the relationship to ondansetron is unclear (PDR, 2000).

Ondansetron is classified as pregnancy category B. Although no adverse events or teratogenic effects have been reported in pregnant women, pregnant women will be excluded from participation and taken off study if they become pregnant.

Subjects will be cautioned not to take concomitant medications, whether prescription, OTC medications, or herbal supplements without consulting the study investigator or physician designee.

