12.3 SUBJECT ENROLLMENT AND RANDOMIZATION

If the prospective subject meets all of the study inclusion, does not meet the exclusion criteria (a checklist will be provided in the CRFs), and has signed the informed consent form, then the subject can be enrolled onto the study. Investigators or study coordinators will submit a subject randomization form to the data coordinating center to receive the subject's random dose code number. The randomization form will contain all information pertinent to the stratification variables for treatment assignment. The data coordinating center will then return to the site, a random dose code number which assigns the participant to a dose level.

If, any subject does not actually receive any investigational agent after they have been randomized, they are considered to be a randomization failure. A randomization failure notification will be submitted to the NIDA data coordinating center so that the coordinating center can reassign that random dose code to another participant.

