12.4 TREATMENT PHASE

On the first day that dosing is scheduled and before dosing occurs, all subjects will have urine collected for methamphetamine and creatinine testing, and then the subject will be given the first dose of the investigational agent in the clinic regardless of the time and will be observed for one hour to monitor for immediate adverse symptoms.

Depending on the treatment arm to which subjects were assigned, subjects will receive 0.25, 1.0 or 4.0 mg ondansetron or matched placebo twice a day.

Subjects will be scheduled for assessments three times per week usually on a Monday, Wednesday, and Friday for 8 weeks. Two consecutive days may be scheduled around holidays or other schedule conflicts. All subjects will be offered an opportunity for HIV testing and counseling and HIV/AIDS education (Appendix II). All subjects will be provided with manual-guided CBT three times per week during the 8 weeks of treatment. Clinical evaluations are described in detail in section 13.0.

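### The entry pregnancy test can be up to 28 days old at enrollment, and no repeat is required before the first dose

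*Protocol*

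**What the plan says.** Inclusion criterion 6 (section 9.1) offers women this route to entry: "Be female and have a negative pregnancy test and agree to use one of the following methods of birth control". Exclusion 16 (section 9.2) bars anyone who would "Be pregnant or lactating". Neither sets a time limit for the test. Section 10.6 gives the intent: "pregnant women will be excluded from participation and taken off study if they become pregnant".

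The synopsis fixes the schedule: "a pregnancy test will also be performed during screening, at study week 4, and at study termination". Table 1 and sections 13.3, 13.4 and 13.6.11 agree. Section 13.3 prefers the first visit of week 4 for the mid-treatment test. Section 12.2 sets the validity period for screening results: "Screening assessments are considered valid if the subject enrolls on the study within 4 weeks". No shorter limit is given for the pregnancy test.

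On the first dosing day, section 12.4 requires that "before dosing occurs, all subjects will have urine collected for methamphetamine and creatinine testing". Sections 13.3 and 13.6.20 add the weekly toxicology screens to the first urine of each treatment week. No pregnancy test is listed for that specimen. Section 13.6.20 describes the pregnancy test as an on-site urine device.

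**The concern.** A stated exclusion is confirmed by a result that can be several weeks old when exposure starts. A site that follows the plan exactly can give the first dose to a woman who would test positive that day, and the next scheduled look comes about three weeks into treatment. Urine is collected three times a week through baseline and again before the first dose, and the device is already on site, so the gap exists only because no test is scheduled on those specimens. What is at stake is fetal exposure that the protocol means to avoid.

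**Working it through.** **Age of the clearing test.** Section 12.2 gives a maximum of 4 × 7 = 28 days at enrollment. A test at the start of a normal two-week baseline is about 14 days old. Table 1 allows the test anywhere in weeks -4 to 0, so it can also be more recent. The protocol sets no maximum interval from randomization to first dose, so 28 days is a ceiling at enrollment and not strictly one at dosing.

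**Time on drug before the next test.** Count day 1 as the first dose and study weeks as seven-day blocks. Week 4 is then days 22-28.
- Preferred first visit, day 22: 22 - 1 = 21 days elapsed.
- Last week-4 visit on a Monday/Wednesday/Friday schedule: 25 days elapsed for a Monday start (day 26), 26 for a Wednesday or Friday start (day 27).
- Outer bound, day 28: 27 days, which needs an atypical schedule.

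**Gap between scheduled tests** (no delay between enrollment and dosing, preferred week-4 visit): 14 + 21 = 35 days in the normal case, 28 + 21 = 49 at most. With a day-1 test it is 21.

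**Women exposed.** Section 9 requires at least 30% women at each site, and about 180 subjects are planned: 0.30 × 180 = 54. Three of the four arms are active: 54 × 3/4 = 40.5 on ondansetron.

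**Pregnancies a repeat test would newly detect.** Both tests share the same blind period after conception, so a repeat moves the detection window forward by the age of the old test. At a constant rate:

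expected number = women on ondansetron × share able to conceive × (test age / 365) × annual failure rate

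The failure rate (5-18% per year) and the share able to conceive are assumptions; neither is in the protocol.

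| Test age | Share able to conceive | At 5% | At 18% |
|---|---|---|---|
| 14 days | half | 40.5 × 0.5 × 14/365 × 0.05 = 0.039 | × 0.18 = 0.140 |
| 14 days | all | 40.5 × 14/365 × 0.05 = 0.078 | × 0.18 = 0.280 |
| 28 days | half | 40.5 × 0.5 × 28/365 × 0.05 = 0.078 | × 0.18 = 0.280 |
| 28 days | all | 40.5 × 28/365 × 0.05 = 0.155 | × 0.18 = 0.559 |

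Since 54 is a minimum, take instead 50% women (an assumption): 90 women, 67.5 on ondansetron. With half able to conceive and a 28-day-old test, the result is 67.5 × 0.5 × 28/365 × 0.05 = 0.129, or 0.466 at 18%.

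**What a repeat would still miss.** With an assumed 14-day blind period, all women able to conceive: 40.5 × 14/365 × 0.05 = 0.078, or 0.280 at 18%. With half able to conceive: 0.039-0.140.

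**The case against.** The strongest case against is that nothing here is contradictory. A four-week validity window for screening results, with tests before, during and after treatment, is an ordinary choice. Contraception is required and checked by a physician (section 13.6.4), a study physician reviews adverse events weekly (13.6.28), ondansetron is category B with no teratogenic effects reported (10.6), and a site may repeat the dipstick at its own discretion. With a 14-day-old test and a 14-day blind period, the fix misses as many pregnancies as it catches.

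Most of this stands and limits the weight of the point. It does not remove the gap: none of these safeguards re-confirms exclusion 16 close to the first dose, a discretionary test is not a required one, and no drawback of testing later has been shown.

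A reader might go further, and the protocol does not support it:
- That it contradicts itself: the schedule is the same wherever it appears.
- That 28 days is the typical age of the test: it is the maximum, reached only if the test is done early and enrollment comes at the end of the window.
- That women routinely spend 27 days on drug before retesting: the stated preference points to about 21.
- That the day-1 urine is tested for methamphetamine and creatinine alone: toxicology screens also apply to the first urine of the week.

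**Conclusion.** The point holds as a minor safety gap. The clearing test may be up to 28 days old at enrollment (about 14 in the normal case), no repeat is required before dosing, and the next scheduled test comes about 21 days after the first dose, or up to 25-27 if done later in week 4. The most reasonable estimate of benefit is 0.04-0.14 newly detected pregnancies on ondansetron across the trial, with an upper case of 0.16-0.56 at the minimum female enrollment. These figures rest on the assumed failure rates, share able to conceive and constant rate of conception. Efficacy is not affected: the intent-to-treat set requires the first day's agent, so a woman found positive before dosing never enters it. The protocol shows no specific harm from the added exposure. The case for change is that the remedy costs almost nothing and makes a stated exclusion current when exposure begins.

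**What to change.** In section 12.4, section 13.6.11, Table 1 and the synopsis, add an on-site urine pregnancy test on urine already collected, either at the last visit before randomization or on the day-1 pre-dose specimen. Require a negative result before the first dose.

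Testing before randomization lets the result be recorded on the Inclusion/Exclusion form before the site "will submit a subject randomization form to the data coordinating center". Testing on day 1 keeps the result current however long the interval since randomization. A woman first positive on day 1 after randomization would become a randomization failure, which section 12.3 already handles by notifying the center "so that the coordinating center can reassign that random dose code to another participant".

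The cost is one extra dipstick per woman (at least 54), a small amendment needing IRB approval before it takes effect, and an occasional dose-code reassignment. No visit or specimen is added. Very recent conceptions would still be missed.

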12.3 SUBJECT ENROLLMENT AND RANDOMIZATION

If the prospective subject meets all of the study inclusion, does not meet the exclusion criteria (a checklist will be provided in the CRFs), and has signed the informed consent form, then the subject can be enrolled onto the study. Investigators or study coordinators will submit a subject randomization form to the data coordinating center to receive the subject's random dose code number. The randomization form will contain all information pertinent to the stratification variables for treatment assignment. The data coordinating center will then return to the site, a random dose code number which assigns the participant to a dose level.

If, any subject does not actually receive any investigational agent after they have been randomized, they are considered to be a randomization failure. A randomization failure notification will be submitted to the NIDA data coordinating center so that the coordinating center can reassign that random dose code to another participant.

12.4 TREATMENT PHASE

On the first day that dosing is scheduled and before dosing occurs, all subjects will have urine collected for methamphetamine and creatinine testing, and then the subject will be given the first dose of the investigational agent in the clinic regardless of the time and will be observed for one hour to monitor for immediate adverse symptoms.

Depending on the treatment arm to which subjects were assigned, subjects will receive 0.25, 1.0 or 4.0 mg ondansetron or matched placebo twice a day.

Subjects will be scheduled for assessments three times per week usually on a Monday, Wednesday, and Friday for 8 weeks. Two consecutive days may be scheduled around holidays or other schedule conflicts. All subjects will be offered an opportunity for HIV testing and counseling and HIV/AIDS education (Appendix II). All subjects will be provided with manual-guided CBT three times per week during the 8 weeks of treatment. Clinical evaluations are described in detail in section 13.0.

12.5 TREATMENT TERMINATION INTERVIEW

After the completion of dosing (as soon as possible after the last dose of investigational agent is taken during study week 8) or at the time of premature treatment termination, subjects will be asked to come to complete a treatment termination interview. Vital signs, physical examination, a 12-lead ECG, pregnancy test and clinical laboratory studies (blood chemistry, hematology, and urinalysis) will be performed. The ASI-Lite, HRBS, CGI-O, CGI-S, MAWQ, cognitive battery, and End of Trial form will be completed in addition to the scheduled weekly assessments. Methamphetamine and creatinine and other drug urine tests, alcohol breathalyzer, and self report of substance use will be completed.

12.6 PREVENTION OF STUDY DROP-OUTS

Subjects will be encouraged to come for treatment and for the evaluation sessions as described in this protocol. To minimize missed sessions, they will be reimbursed for transportation and time spent in completing study assessments. It will be emphasized to subjects during screening that even if they have a relapse they should come to all scheduled appointments. They will be discouraged from using methamphetamine, but there will be no penalty for relapsing or for missed sessions.

Subjects will be encouraged to complete study visits, assessments, and CBT sessions, even if they are unable to tolerate the study medication. If a subject decides to drop out of the study prior to week 8, s/he will be asked to complete all final assessments (termination) at the time of drop out. If a subject wishes to stop taking the study agent but to continue to participate in and CBT sessions, s/he will continue to have all scheduled assessments according to the protocol and will complete the study at week 8. In this case, all study measures will be completed per protocol with the exception of those strictly related to the study agent.

A subject will be considered a drop out, if the subject misses six consecutive sessions during the 8 weeks of treatment. However, s/he will be asked to complete all termination assessments at the time of drop out and will be compensated for completing these assessments.

Subjects are free to discontinue the study and to refuse to participate in any of the procedures. If a subject drops out without making their intentions known, staff will attempt to contact them by telephone or written correspondence. Once the subject has been contacted and expresses their decision to discontinue from further participation in the study, the research staff will cease to try to make further contact.

